8.0 Regulatory Considerations

The study will be conducted in compliance with ICH guidelines and with all applicable federal (including 21 CFR parts 56 & 50), state or local laws.

8.1 Data Storage

Data will be stored electronically on a secure server in a password protected file. Access to data will be restricted with only principal and co-investigators as well as study coordinators and appointed regulatory reviewers having access to the file's contents.

8.2 Adverse Events and Data Monitoring

This protocol is a feasibility study. No clinical adverse events are expected. We will record number of patients who have the ultrasound probe attached during treatment and number of patients who have the ultrasound probe removed. When the treatment completed, no study related follow up is required.

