5.0 Research Plan

5.1 Investigate whether the ultrasound imaging can enhance soft tissue tumor localization.

(a) Following the standard clinical procedure, daily KV-CBCT image for each patient will be acquired and used to guide for patient setup prior to treatment delivery. Because of limited soft tissue contrast in KV-CBCT to observe the soft tissue organ, such as the prostate, the added ultrasound image may enhance soft tissue localization prior to treatment for these patients.

The ultrasound device will be calibrated to the treatment iso-center via an external camera system and infrared markers on the ultrasound (US) probe. A commercially available passive arm will be acquired and attached to the ultrasound probe. Following our current clinical protocol, the patient treatment position will be determined solely based the daily KV-CBCT. After KV-CBCT guidance, a pre-treatment US image will be acquired for the study but not used for patient positioning. The success of this specific aim is defined as that the tumors can be visualized in the ultrasound images in at least 80% of patients enrolled.

(b) Investigate whether the presence of a passive arm will interfere with radiation delivery during each treatment.

In order to monitor tumor or organ motion during radiation, the US probe will be placed using a passive arm, as shown in the figure below. This passive arm will be attached to the treatment couch and also in contact with the patient during the radiation. Although the passive arm is commercially available, we plan to test whether the presence of the US probe will interfere radiation delivery during each treatment. Specifically, we will test: (a) whether the passive arm reduces the clearance between the patient and the gantry of the linear accelerator; (b) whether the passive arm can hold a consistent contact pressure with the patient under normal breathing motion; (c) whether the passive arm can be automatically released if a patient makes a large movement. The success of this specific aim is defined as that at least 80% of patients are able have the ultrasound probe attached during the entire treatment course.

Figure 1.

(c) Investigate whether the presence of the ultrasound probe will interfere with the choice of radiation beams and degrade plan quality

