6.0 Study Parameters

The study parameters collected are the US images acquired prior to each treatment and during radiation delivery. Pre-treatment KV-CBCT images will also be collected for dosimetric analysis. Specifically, the tumor location detected from combined US/KV-CBCT images will be compared with using KV-CBCT alone. Using the KV-CBCT the gold standard, 3D radiation dose distributions will be re-calculated according to the tumor localizations using KV-CBCT alone and using combined US/KV-CBCT. For SBRT prostate cancer, we will compare the following dosimetric endpoints, extracted from dose volume histograms.

Organ Name	Endpoint 1	Constraints
PTV_HD*	V5000 cGy	> 50%
PTV_LD*	V3625 cGy	> 95%
PROSTATE	V3625 cGy	> 95%
BLADDER	D0.03 cc	< 5250 cGy
RECTUM_ANT	D0.03 cc	<5000 cGy
RECTUM_LAT	D3cc	< 4000 cGy
RECTUM_POST	V0.03 cc	< 2250 cGy
URETHRA	V0.03cc	< 5000 cGy
URETHRA	D1cc	< 4500 cGy

PTV_HD = planning target volume in high dose prescription dose of 5000 cGy

PTV_LD = planning target volume in low prescription dose of 3625 c Gy.

For patients treated with conventional multiple fractionation, we will compared the following dosimetric endpoints, extracted from dose volume histograms.

Organ Name	Endpoint 1	Constraints	Planned	comments
CTV_7800	V7800 cGy	> 99%		
PTV_7800	V7800 cGy	> 95%		
BLADDER	V7000 cGy	< 10%		
BLADDER	V6000 cGy	< 20%		
RECTUM	V7000 cGy	< 10%		
RECTUM	D10cc	< 7000 cGy		
RECTUM	V5000 cGy	< 30%		Without pelvic nodes
RECTUM	V5000 cGy	< 50%		With pelvic nodes
FEMORAL HEAD_L	V5000 cGy	< 5%		
FEMORAL HEAD_R	V5000 cGy	< 5%		
PENILE BULB	Dmean	< 5250 cGy		

For patients with prostatectomy receiving post-operative radiotherapy with conventional multiple fractionation, we will compared the following dosimetric endpoints, extracted from dose volume histograms.

Organ Name	Endpoint 1	Constraints	Planned	comments
CTV_7000	V7000 cGy	> 99%		
PTV_7000	V7000 cGy	> 95%		
BLADDER	V6500 cGy	< 40%		
BLADDER	V4000 cGy	< 60%		
RECTUM	V6300 cGy	< 10 %		
RECTUM	D10 cc	<6300 cGy		

RECTUM	V4500 cGy	< 30 %		Without Pelvic nodes
RECTUM	V4500 cGy	< 50%		With pelvic nodes
FEMORAL HEAD_L	V5000 cGy	< 5%		
FEMORAL HEAD_R	V5000 cGy	< 5%		
PENILE BULB	Dmean cGy	< 5250 cGy		

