7.0 Statistical Considerations

Because of limited funding from NIH, the number of patients that are planned to be enrolled into this protocol will be small and potentially lacking of the statistical power. The primary purpose of this study is a feasibility study to test whether a combined CBCT and ultrasound image guidance is clinically feasible. Our analysis is primarily descriptive and does not require any advanced statistics to analyze the endpoints. As a measure of protocol success we expect that:

- 1) Over 80% of patients have ultrasound images which are clinically adequate for treatment set-up in the judgment of the treating physician.
- 2) Over 80% of patients are able to undergo ultrasound based tumor tracking during treatment.
- 3) The quality of treatment plans for more than 80% of patients will not be affected.
- 4) No adverse events related to the ultrasound probe are noted during treatment.

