8.4 Sources of Materials

The research project will involve acquiring ultrasound images in addition to the standard x-ray images acquired for the treatment procedures. All other medical records and data will also be collected per standard practice to manage the treatment of the patient.

The medical records and data collected during the studies will consist of identifiable information that can be linked back to the patient (e.g. patient names, treatment dates, history numbers, dates of progression and/or response). We will obtain privacy authorizations from patients before we collect and store data and medical information. Only the research team listed in this proposal will have access to the subjects' identities and any data or records disclosed to a third party will be de-identified.

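### Aim 5.1(b) promises to test clearance, contact pressure and automatic release, but it is scored and recorded on attachment alone, so a failed release or an arm-gantry contact can go unseen

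*Combined protocol and SAP*

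**What the plan says.** Section 5.1(b) acknowledges that the arm is a commercial product but still plans to test it across treatments. It names three sub-tests: "whether the passive arm reduces the clearance between the patient and the gantry of the linear accelerator"; whether contact pressure stays consistent under normal breathing; and "whether the passive arm can be automatically released if a patient makes a large movement". The success rule that closes the paragraph is that "at least 80% of patients are able have the ultrasound probe attached during the entire treatment course".

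Four other places bear on what is recorded or judged:

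- **8.2:** "We will record number of patients who have the ultrasound probe attached during treatment and number of patients who have the ultrasound probe removed". It states that no clinical adverse events are expected.
- **6.0:** "The study parameters collected are the US images acquired prior to each treatment and during radiation delivery". KV-CBCT images and dose endpoints are added; no item describes the arm.
- **7.0:** criterion 2 asks that over 80% of patients can undergo ultrasound tracking, and criterion 4 reads "No adverse events related to the ultrasound probe are noted during treatment".
- **8.5:** a dry run before treatment checks clearance between arm and gantry.

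Section 5.1(c) adds that the probe is taken off before treatment when the physician judges that the altered beam angles harm the plan. Those patients leave aims (b) and (c), which is expected to be rare. No section defines a large movement.

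**The concern.** Automatic release is the arm function that matters when a patient moves with a couch-mounted probe pressed against the body during irradiation. The protocol singles it out for testing, then scores the aim on a quantity that does not depend on whether release works. A failed release leaves the probe where it was, and so does an arm-gantry contact after which treatment carries on. Neither event lowers the attachment rate.

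At stake is what the study can say at its end. Aim (b) could be declared met while one of its three stated tests has no numerator, no denominator and no pass criterion. Section 8.8 expects the feasibility data to inform a later treatment protocol, and that protocol would inherit an attachment rate that is uninformative about release.

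**Working it through.** The documents give no power, alpha or event rate for this aim, so there is no stated figure to reproduce. The check has two parts: a comparison of the sections, and arithmetic on the 80% rule.

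**1. Each sub-test against the rule and the record**

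| Sub-test in 5.1(b) | Term in success rule | Item in 8.2 or 6.0 | Partial evidence elsewhere |
|---|---|---|---|
| Gantry clearance | none | none | Dry run (8.5), before treatment only |
| Contact pressure | none | none | Images during delivery may show lost contact |
| Release on large movement | none | none | Images may show lost contact, but not a failed release |

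The removed count in 8.2 cannot stand in for release. It does not separate automatic release from removal by staff, or from the planned removal in 5.1(c). A failed release after which the probe stays on appears in the attached count.

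**2. Threshold for aim (b)**

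With n = 30 (section 3.0), the rule needs 0.80 × 30 = 24 patients attached, so it fails once 30 − 24 + 1 = 7 are not. The *over 80%* wording of criterion 2 in 7.0 would need 25.

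**3. The same 7 patients under each scoring**

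Seven large movers is an assumption chosen because it is where the rule switches. All other patients are taken as attached throughout.

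| Scoring | Arm releases correctly in all 7 | Arm fails to release in all 7 |
|---|---|---|
| Release ends attachment | 23/30 = 76.7%, fails | 30/30 = 100%, passes |
| Re-attachment counts as attached | 30/30 = 100%, passes | 30/30 = 100%, passes |
| Proposed rule (see fix) | 30/30 = 100%, passes | 23/30 = 76.7%, fails |

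If 5.1(c) removed 3 patients (also an assumption), n = 27, the rule needs 22 (0.80 × 27 = 21.6), and the switch comes at 6 patients: 21/27 = 77.8%.

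**4. Range over the unknown movement rate**

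Let q be the share of patients with at least one large movement. Assume 95% would otherwise stay attached, and that release ends attachment. For a correctly releasing arm the chance of meeting the rule is P(X ≥ 24), with X binomial(30, 0.95 × (1 − q)). For an arm that never releases it is P(X ≥ 24) with probability 0.95.

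| q | Releases correctly | Never releases |
|---|---|---|
| 5% | 0.977 | 0.999 |
| 10% | 0.866 | 0.999 |
| 20% | 0.396 | 0.999 |
| 30% | 0.081 | 0.999 |

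If re-attachment counts, both columns are 0.999 at every q. On neither reading does failure to release lower the score.

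**5. What a release result could show**

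With no failures in m large movements, the one-sided 95% exact upper bound on the failure rate is 1 − 0.05^(1/m): 63% for m = 3, 45% for m = 5, 26% for m = 10 and 9.5% for m = 30. Since m is not recorded, not even this bound could be reported.

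**The case against.** The strongest reply is that the 80% rule is a feasibility threshold worded as ability. A patient whose arm releases once and is re-attached may still be able to complete the course with the probe on, and the documents never say that a release ends attachment. This stands. A reader might infer that the rule positively rewards an arm that fails to release, but that follows only on one of two permissible readings. What holds on both is that the rule does not see release.

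Second, evidence may lie elsewhere. Images are collected during delivery, criterion 2 in 7.0 asks for tracking rather than mere attachment, and criterion 4 would fail the study on a probe-related injury. Section 8.0 says "The study will be conducted in compliance with ICH guidelines", and 8.4 says "All other medical records and data will also be collected per standard practice", so an interruption may well be charted. Poor clearance found at the dry run would probably lead to the probe being left off. A reader should therefore not infer that oversight is absent. But a failed release can look like uninterrupted tracking, a failed release without injury need not be an adverse event, and none of these sources makes release a study outcome.

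Third, whether the arm can release is partly a capability question, which a check without a patient could answer. That is fair, and the fix allows it. The protocol describes no such check: its dry run covers clearance only.

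Fourth, the study is small and calls its analysis mainly descriptive. That argues against demanding precision, but a descriptive study still depends on what it records.

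**Conclusion.** The point holds as a mismatch between what aim (b) sets out to test and what it scores and records. The success rule is blind to failed release, and to arm-gantry contact during delivery unless the probe is then taken off. An arm that never releases can meet aim (b). This rests on the text alone and needs no assumed event rate.

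The adverse direction is conditional. Only if a release ends attachment is a correctly releasing arm penalised, and the size then depends on movement rates that the documents do not give. The 7-of-30 example and the values of q are illustrations, not forecasts.

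A reader might also infer that the next protocol will take the attachment rate as proof that the arm releases. Section 8.8 does not say so; it speaks of the feasibility data in general, after a sentence on recalculated dosimetry.

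This is more than a drafting clarification, because the scoring decides what aim (b) can conclude. It does not prevent the study from running.

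**What to change.** **In 8.2**, for each fraction with the arm in place, record:

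- any large patient movement, with a working definition;
- whether the arm released;
- any arm-gantry contact during delivery;
- any loss of probe contact under normal breathing.

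Record automatic release separately from removal by staff and from the planned removal in 5.1(c).

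**In 5.1(b)**, state that a correct release followed by re-attachment counts as attached, and that a failed release or an arm-gantry contact during delivery is not a success for that patient.

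**In reporting**, give releases over large movements descriptively, with an exact interval, beside the attachment rate. If few movements occur, state that release could not be assessed in patients, or check it without a patient, for example by adding a release check to the existing dry run.

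**Cost:** a few tick-box items per fraction, a definition to agree, and a scoring sentence or two. No extra patients or visits are needed. Aim (b) may score lower, and the release estimate will be imprecise if movements are rare.

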8.3 Written Informed Consent

Provision of written informed consent must be obtained prior to any study-related procedures. The Principal Investigator will ensure that the subject is given full and adequate oral and written information about the nature, purpose, possible risks and benefits of the study as well as the subject's financial responsibility. Subjects must also be notified that they are free to discontinue from the study at any time. The subject should be given the opportunity to ask questions and be allowed time to consider the information provided.

The original, signed written Informed Consent Form must be kept with the Research Chart in conformance with the institution's standard operating procedures. A copy of the signed written Informed Consent Form must be given to the subject. Additionally, documentation of the consenting process should be located in the research chart.

8.4 Sources of Materials

The research project will involve acquiring ultrasound images in addition to the standard x-ray images acquired for the treatment procedures. All other medical records and data will also be collected per standard practice to manage the treatment of the patient.

The medical records and data collected during the studies will consist of identifiable information that can be linked back to the patient (e.g. patient names, treatment dates, history numbers, dates of progression and/or response). We will obtain privacy authorizations from patients before we collect and store data and medical information. Only the research team listed in this proposal will have access to the subjects' identities and any data or records disclosed to a third party will be de-identified.

8.5 Potential Risks

Other than the potential of mild discomfort from the placement of the ultrasound probe, there is no risk associated with the additional on-board ultrasound imaging. During treatment planning, we will make sure that the US probe and the passive arm are not blocking the radiation beams, and conduct a run dry run (before radiation treatment) to make sure adequate clearance between the passive arm and the gantry of the linear accelerator.

All other potential risks are associated with the standard clinical practice of radiation treatment. These will be managed with established procedures in place.

8.6 Protection Against Risk

No adverse effects are expected from the additional ultrasound imaging in the research.

Protections against Breach of Confidentiality:

All research personnel involved in this study will comply with HIPAA regulations. The following measures will be taken to minimize the risk of breaching patient confidentiality:

- Patients' clinical data (hard and soft copies) will be stored in electronic format and stored in a password protected server located in a locked server room at main Campus of Cleveland Clinic.

- Only research staff and authorized regulatory agencies will have access to the data. The secured data includes: case report forms, source documentation, signed consent forms, and any material containing patient identifying information.
- This data will be securely stored in electronic format in Cleveland Clinic and data pertinent to this protocol will be stored in a password protected server that is located in a locked server room.
- No information by which patients can be identified will be published.

8.7 Potential benefits of the proposed research to the subjects and others

There is no additional benefit to the study participants. However, participants could potentially receive an indirect benefit of a feeling of altruism knowing their participation will pave the way for future patients whose treatment may be guided by the integrated 3D x-ray/ultrasound imaging system.

8.8 Importance of the knowledge to be gained

The research aims to develop a novel non-invasive approach of image guidance of hypofractionated SBRT of patients with abdominal and pelvic tumors with the capability of continuous monitoring during radiation delivery. Successful monitoring of target position during treatment is expected to reduce margins required during radiation treatment, and thereby reduce dose to surrounding normal tissue. This has been demonstrated clinically using real-time tracking technology using implanted markers in prostate cancer, but in this study would be able to be done non-invasively using ultrasound.

The analysis of the recalculated dosimetry will show the uncertainty of dose delivery using current CBCT and ultrasound image guidance methods and shed light on the degree of improvement that can be achieved when they are combined. The data from the feasibility studies will be immensely useful for designing a treatment protocol with adequate statistical power to prove the improvement in treatment accuracy and efficacy. In turn, a cost-benefit analysis can then be made in terms of resource allocation, treatment efficiency and margin reduction. The information will be most significant as a baseline for assessing the cost-effectiveness of the next generation of advanced IGRT machines such as those employing on-board MRI.

8.9 Retention of records

The Principal Investigator of The Case Comprehensive Cancer Center supervises the retention of all documentation of adverse events, and all correspondence for as long as needed to comply with national and international regulations. No records will be destroyed until the Principal Investigator confirms destruction is permitted.

